NOTE: During Visit 1 if the IOP is elevated based on the criteria outlined below by glaucoma specialists, the subject will be asked to skip Visit 2 and will be eligible to continue to Visit 3 with the local ophthalmologist. The subject will sign the Part II consent and get randomized during Visit 1. They will also complete the NEI-VFQ-25. If the subject chooses not to continue with the study, the team along with the PCP will make sure to stress the importance of seeing an ophthalmologist of their choosing in the time frame outlined.

IOP in either eye  $> 30\text{ mm Hg}$  subject to visit ophthalmologist within 2 weeks  
 IOP in either eye  $> 35\text{ mm Hg}$  subject to visit ophthalmologist within 1 week  
 IOP in either eye  $> 40\text{ mm Hg}$  subject to visit ophthalmologist within 1 day

A Wills Eye Hospital ophthalmologist will call a local eye care provider to advise them of the elevated eye pressure and the need for a timely appointment.

When images are received at WETD, a trained reader reviews the data and confers with the glaucoma and/or retina specialist, who determines if clinical pathology merits further evaluation and treatment and establishes relevant diagnoses. In addition to glaucomatous changes and DR, ocular hypertension, cataract, branch retinal vein and arterial occlusion, central retinal vein and arterial occlusion, epi-retinal membrane, macular degeneration, drusen and pigmentary disturbance will be documented on the report. Reports (Appendix F) are

uploaded to a secure password-protected, HIPAA-compliant web site, where the PCPs can access these records and link the report to their own patient’s medical record. Patients with ocular pathology or patients who have photographs that are unreadable will be contacted and scheduled within 1-2 months for Visit 2 to confirm the diagnosis. Any patient with emergency eye issues, such as a detached retina, will be called immediately and scheduled for Visit 2. The patient’s PCP will also be notified by phone immediately and a follow-up letter will be sent to the patient’s home.

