**C.5.d. Ongoing Education/Training/Fidelity:** Extensive training will take place during Phase 1 to ensure that all research staff adhere to policies and procedures. The Director of the Department of research and Glaucoma research center will be responsible for training Wills Eye Department of Research staff in cultural competency. The Director of Operations for Wills Eye Hospital’s Telemedicine Department will be responsible for ongoing training on the Volk Pictor Plus camera for all ocular technicians and study staff. Glaucoma specialists will be trained to read the optic nerve images. Study Investigators will develop letters to send to local ophthalmologists to inform them about the study and invite them to participate. In addition, but before we begin the study, in conjunction with our general ophthalmology advisor, we will plan and develop definitions of adherence for all patients during Visits 3-8.

**C.6. Visit 2: Baseline Assessment Measures and Confirming Diagnosis (PCP Office):** Patients who have been diagnosed with glaucoma, glaucoma suspect, other eye diseases, vision impairment or have photographs that are unreadable who require non-emergent follow-up, will be notified by mail and telephoned by the study staff to schedule Visit 2 within 4 weeks of the detection visit. We will call all patients to remind them of the exam, discuss steps to prepare for an eye exam, and answer any questions. There will be no cost for this comprehensive eye exam. Any patient with an emergency eye issue at Visit 2 will be contacted immediately by phone and scheduled for an appointment at Wills Eye Hospital.

To conduct Visit 2, a leased van will transport the research team and all necessary equipment to the site each day. During the visit, an ocular technician and a glaucoma specialist will assess the patient’s ocular, systemic, and family history and conduct a undilated eye exam including: 1) visual acuity measurement using Snellen eye charts, 2) slit-lamp biomicroscopy of the anterior segment, 3) IOP, 4) undilated optic nerve head evaluation (although if patient has diabetes they may be dilated),5) central corneal thickness measurement, 6) visual field analysis using the Octopus visual field analyzer and 7) gonioscopy.

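### An emergency found on Visit 1 images is booked into Visit 2 with no time to examination, and the two protocol sections on emergencies do not agree on where the patient goes

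*Combined protocol and SAP*

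**What the plan says.** Section C.5.c (Visit 1, PCP office) describes image review. A trained reader "confers with the glaucoma and/or retina specialist, who determines if clinical pathology merits further evaluation and treatment and establishes relevant diagnoses". Patients with ocular pathology or unreadable photographs "will be contacted and scheduled within 1-2 months for Visit 2 to confirm the diagnosis". The exception follows: "Any patient with emergency eye issues, such as a detached retina, will be called immediately and scheduled for Visit 2". The text adds that the "PCP will also be notified by phone immediately and a follow-up letter will be sent to the" patient's home.

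The same section treats high IOP at Visit 1 differently. Those patients skip Visit 2, sign the second consent, are randomized and complete the NEI-VFQ-25 at Visit 1. They then see a local ophthalmologist within 2 weeks (above 30 mm Hg), 1 week (above 35) or 1 day (above 40); the last rule reads "subject to visit ophthalmologist within 1 day".

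Section C.6 (Visit 2, PCP office) covers patients "who require non-emergent follow-up, will be notified by mail and telephoned by the study staff to schedule Visit 2 within 4 weeks", counted from Visit 1. It then states: "Any patient with an emergency eye issue at Visit 2 will be contacted immediately by phone and scheduled for an appointment at Wills Eye Hospital". Staff and equipment come to the site by van, and a technician and a glaucoma specialist carry out what C.6 describes as an undilated exam.

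**The concern.** The plan itself classes a detached retina as an emergency, yet it names as the next step a visit at the primary care office and does not say by when the patient must be examined. The hospital appears as a destination only one step later. Two staff members applying the protocol in good faith could send the same patient to different places: one to Visit 2 under C.5.c, the other to Wills Eye Hospital under C.6. Patient safety is at stake here, not the validity of the trial's estimates.

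**Working it through.** There is no figure in the plan to reproduce. The check sets the sections side by side.

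**1. Stated times to examination**

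| Situation | Section | Destination | Limit |
|---|---|---|---|
| IOP above 30 mm Hg at Visit 1 | C.5.c | Ophthalmologist, Visit 2 skipped | 2 weeks (14 days) |
| IOP above 35 mm Hg at Visit 1 | C.5.c | Same | 1 week (7 days) |
| IOP above 40 mm Hg at Visit 1 | C.5.c | Same | 1 day |
| Pathology or unreadable image | C.5.c | Visit 2 | 1-2 months |
| Non-emergent follow-up | C.6 | Visit 2 | 4 weeks |
| Ocular disease | B.6 | Exam in the same location | 1 month |
| Emergency on Visit 1 images | C.5.c | Visit 2 | none stated |
| Emergency at Visit 2 | C.6 | Wills Eye Hospital | none stated |

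The count of examination limits is 3 for high IOP, 0 for an image emergency at Visit 1 and 0 for an emergency at Visit 2. None of the three routine Visit 2 windows is an emergency limit.

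**2. What the word immediately covers.** In C.5.c it governs the call to the patient and the call to the PCP. Even if it is stretched to cover the booking, it does not say when the patient is seen.

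**3. Two readings of the C.6 emergency sentence**

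- *Literal.* It applies to emergencies discovered at Visit 2. A Visit 1 image emergency then goes to the PCP office first and to hospital only afterwards.
- *As a slip.* The sentence phones a patient who would already be in the room, and it stands in the paragraph about scheduling. It may have been meant for emergencies found before the visit. Then C.5.c says Visit 2 and C.6 says Wills Eye Hospital for the same patient.

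Either reading needs a correction, and neither gives a deadline.

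**4. Is there another release clause?** C.9 allows an earlier date at the glaucoma specialist's discretion, but for Visit 3, after a completed Visit 2. No such clause is given for Visit 2.

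**5. What bypassing Visit 2 would touch.** C.9 randomizes patients who have consented and completed Visit 2. The primary Aim 1 analysis in E.2.a counts patients given a diagnosis of glaucoma or glaucoma suspect and confirmed at Visit 2. A retinal emergency alone would therefore enter only the repeat analysis of any eye pathology.

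**The case against.** The strongest reply is that the protocol already has a faster track. A specialist sees the images, the patient and PCP are phoned at once, and nothing forbids a direct hospital referral. The C.6 sentence plausibly supplies the hospital as destination. This reply stands in part: the safeguards are real and make a long delay less likely. They still leave place and time unstated, and the C.6 sentence as written does not cover Visit 1.

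Four stronger readings are tempting and are not supported.

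- A reader might infer that an emergency waits 1-2 months. It does not: the emergency sentence is an exception to that rule.
- A reader might infer that C.6 defines Visit 2 as a non-emergent visit. That phrase describes the patients on the routine track, not the visit.
- A reader might infer that Visit 2 cannot assess the retina, since the seven items listed in C.6 include nothing retinal beyond the optic nerve head. But the list is not presented as exhaustive, patients with diabetes may be dilated, and the section also says "There will be no cost for this comprehensive eye exam". Table 5 ticks a complete eye exam at Visit 2, diabetic retinopathy is to be diagnosed there, and B.6 calls the exam dilated. The content of the exam is unclear rather than shown to be inadequate.
- A reader might infer that handling image emergencies differently from IOP is itself an error. IOP is a number measured on site, while an image finding needs judgement. The IOP rules show only that a bypass with deadlines is workable in this trial.

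**Conclusion.** The point holds as a gap and an inconsistency in a safety pathway. C.5.c sends an acknowledged emergency to Visit 2 without a time to examination. Together with C.6, this either puts an intermediate visit before hospital care or leaves the destination in conflict. It should be fixed, because the correction is simple and the plan already contains both a suitable destination and a model for deadlines.

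The size cannot be given in patients or days: the documents report neither how often such emergencies occur nor how long the booking takes. No actual harm or delay is shown.

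The conclusion rests on the main text. The appendices, the consent pages and some other pages were not available and might contain an emergency procedure. Even then, the two main-text sentences would need to be brought into line.

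**What to change.** - **C.5.c:** replace the booking into Visit 2 with a direct urgent appointment at Wills Eye Hospital, within a limit set by the clinical leads. The 1-day rule for IOP above 40 mm Hg is a possible model. Keep the immediate calls to the patient and the PCP.
- **C.6:** reword the emergency sentence so that it covers emergencies found at Visit 1 or Visit 2, with the same destination and limit.
- **Study status:** state, as C.5.c does for high IOP, that these patients skip Visit 2 and that the hospital exam counts as the confirming exam. State also whether, when and where they give the second consent, complete the NEI-VFQ-25 and are randomized, given that C.9 requires a completed Visit 2. The high-IOP wording cannot simply be copied: those patients are consented at Visit 1, whereas an image emergency is reported by phone after the images are read.

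The cost is a few sentences of protocol wording, a staff briefing and access to urgent appointments at the sponsor's own hospital. The downside is that some patients, probably few, are confirmed outside the standard Visit 2 setting. This mainly affects the repeat any-pathology analysis in E.2.a; the primary predictive value for glaucoma and glaucoma suspect is touched only if such a patient also carries one of those diagnoses.

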#### **C.4. Research Design and Methods**

**C.4.a: Project Overview:** The Wills Eye Glaucoma Research Center will conduct a 5-year prospective, randomized controlled trial to evaluate an innovative, community intervention using posterior fundus photographs of the optic nerve and macula to improve access and utilization of eye care to detect, treat, and manage high-risk patients with previously undiagnosed glaucoma, glaucoma suspect, and other eye diseases. L. [name]; [name]; and [name], RD, will lead the research study.

Our diverse targeted, at-risk population includes African Americans, Hispanics, and Asians over age 40; other older adults (aged 65+); individuals over age 40 with a family history of glaucoma and/or with diabetes. Approximately 1250 patients will be recruited from geographically diverse locations across Philadelphia and Chester counties, with the help of our community partners. **Phase 1** will consist of detecting eye disease in 7

primary care offices and 10 FQHC using telemedicine (Visit 1), followed by a comprehensive eye exam by a Wills glaucoma specialist in the same setting to confirm the diagnosis (Visit 2). Based on preliminary data, 30% of patients (approximately 750) will have abnormal optic nerve and/or macula images. The predictive accuracy of the optic nerve images to detect glaucoma and glaucoma suspect as confirmed by the comprehensive eye exam will be evaluated.

**Phase 2** will involve consenting, enrolling, and randomizing 374 patients to either the usual care group (n=187) or the enhanced intervention group (n=187). The enhanced intervention will consist of using patient navigators and a social worker to reduce barriers to follow-up eye care. **Phase 3** will consist of following patients proximally (6 months) and distally (3 years) while they attend appointments with a local, eye care provider (Visits 3-7). Adherence to follow-up recommendations for eye care will be the primary outcome measure. A comprehensive cost study to estimate the intervention costs and cost-effectiveness of detecting eye diseases and vision impairment in a high-risk population will also be conducted. Protocols, materials, outcomes, and results will be disseminated to other communities in order to expand detection of glaucoma, other eye diseases, and visual impairment, and to further refine these approaches to successfully scale the program up to a national level.

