**C.6.a. National Eye Institute-Visual Function Questionnaire (NEI-VFQ):** A member of the research team will consent all patients and administer the validated NEI-VFQ-25 questionnaire at Visit 2, Visit 5 and Visit 8 to assess barriers and the influence of their vision impairment on their health-related quality-of-life. The 12 subscales are calculated by adding the relevant items and transforming the scores into a scale from 0 to 100. Higher scores indicate better quality-of-life. The composite score will be calculated as the average of 12 subscale scores. Patient navigators will use these results to assess barriers and refer patients to appropriate professionals, such as a social worker, low vision specialist, psychiatrist, occupational therapist, Medicare/Medicaid insurance advisor, and/or cataract surgeon. All materials will be culturally and linguistically appropriate and translated into other languages as necessary using trained medical interpreters and we will track all process measures.

\*NEIVFQ surveys will be administered in person to all patients at Visit 2. For Visits 5 and 8 questionnaires will be administered over the phone by a patient navigator or social worker.

**C.6.b. Patient Satisfaction Survey:** With assistance from Westat, our partners, and Advisory Board members, we will create a new survey instrument and administer it at the end of each of the study visits. We will ask patients to rate their satisfaction with the exam, its duration, its convenience, the staff, and the likelihood of attending a follow-up eye exam. These surveys will optimize patient engagement and report outcomes that are important to patients and stakeholders.

\*Satisfaction surveys will be administered in person to all patients for Visits 1 and 2. For Visit 5 surveys will be administered over the phone by a patient navigator or social worker for all enrolled patients. For Visits 3, 4, 6, and 7 satisfaction surveys will be administered according to randomization. For Visit 8 (or final visit), a Study Closeout Satisfaction Survey will be administered at the primary care office by a member of the study team.

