**C.7. Enhanced Intervention Versus Usual Care Group:**

*Group 1: Enhanced Intervention Group with Patient Navigation and Social Worker:* Patients randomized to Group 1 will be provided a list of eye care providers to choose from for follow-up. Patients can also choose to follow-up with an eye care provider not on our list. In that instance we would require a record release to be signed by the patient for the purpose of having access to their follow-up records throughout the study. Prior to all follow-up visits, patients in the enhanced group who have scheduled an appointment will receive a personal phone call reminding them to attend. These patients will receive any necessary interpretation services and educational materials.

*Group 2: Usual Care:* Patients randomized to Group 2 will be recommended to follow-up for eye care with a local eye care provider. These patients will be provided a list of eye care providers to choose from for follow-up. Patients can also choose to follow-up with an eye care provider not on our list. In that instance we would require a record release to be signed by the patient for the purpose of having access to their follow-up records throughout the study. Group 2 represents a realistic choice currently available for patients. Practice patterns will vary depending on the resources, staff time, and services available within each local eye care providers practice.

**C.7.a. Sample Size Determination:** As shown in Figure 1, we have based our sample-size calculations on the current preliminary CDC-project results as well as telemedicine statistics. We project that 30% of those fundus photographs will be abnormal and that, of those, 40% of patients will likely agree to consent and enroll in the study. These patients will be randomized to either the Enhanced Intervention Group 1 or Usual Care Group 2.

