**Table 9: Assessment of Adherence to Follow-Up Recommendations**

Recommended Follow-up	Number of visits per year considered adherent to recommendations
1-2 months	At least 6 visits per year with an eye care provider
3-6 months	At least 3 visits per year with an eye care provider
6 months	At least 2 visits per year with an eye care provider
12 months	At least 1 visit per year with an eye care provider

E.2.c. Primary Analysis for Aim 2: The primary outcome of the study is adherence to recommended follow-up in each year as described in section E.1.c. For each of the 3 years of follow-up, we have a dichotomous measure of adherence. We will model this longitudinal dichotomous outcome using Poisson regression within a generalized estimating equation (GEE) framework. Our model will include time (Year 1, 2, and 3), randomization assignment, randomization by treatment interaction, and baseline individual characteristics believed to be associated with adherence to follow-up, including age, diagnosis, vision impairment, and overall vision-related quality-of-life. Within this model, we will test 2 hypotheses.

First, we will compare randomization groups at Year 1 to test whether there are differences in early adherence. Second, we will calculate the average effect of randomization across Years 2 and 3 and test the long-term efficacy of the intervention. In both cases, we will estimate the overall relative risk of adherence along with its associated confidence interval. Each test will be performed with alpha=0.025. The primary analysis will include all patients who were randomized and have some adherence data (see section on missing data below).

E.2.d. Power for the Primary Analysis for Aim 2: Our estimated available sample size is given in Figure 2. We will randomize 300 patients (150 per group). Assuming up to 10% dropout where adherence cannot be calculated due to death or study withdrawal (i.e., final analysis dataset of n=135 per group), we calculate power to detect a 20% improvement in adherence under various assumptions of adherence under Usual Care. We have greater than 80% power to detect these differences using a two-sided chi-square test with alpha=0.025 (Table 10).

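### C.6.a and C.6.b let navigators and the social worker reach usual-care patients, which may narrow the adherence contrast by an unknown amount

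*Combined protocol and SAP*

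**What the plan says.** **The intervention.** C.4.a defines the enhanced arm by its use of patient navigators and a social worker to lower barriers to follow-up. C.7 puts navigation and social work in the title of Group 1 and lists neither for Group 2, of which it says: "Group 2 represents a realistic choice currently available for patients". C.8.a describes the social worker as contacting patients in the enhanced arm.

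**The questionnaires.** C.6.a gives the NEI-VFQ to all patients at Visits 2, 5 and 8, partly to assess barriers. It then says: "Patient navigators will use these results to assess barriers and refer patients to appropriate professionals, such as a social worker". The list of professionals goes on to include an insurance advisor and a low vision specialist. No arm is named. On who collects the data, C.6.a says: "For Visits 5 and 8 questionnaires will be administered over the phone by a patient navigator or social worker". C.6.b, on the satisfaction survey, is explicit: "For Visit 5 surveys will be administered over the phone by a patient navigator or social worker for all enrolled patients".

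**Where the arms are kept apart.** For the satisfaction survey at Visits 3, 4, 6 and 7, C.6.b follows randomization: usual care by mail, intervention by a call from a navigator or social worker.

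**The last questionnaire.** The closeout list in C.4.a places the NEI-VFQ at the final primary care visit, whereas C.6.a has it given by phone.

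**Outcome and power.** The primary outcome for Aim 2 is attendance at Visit 4 and later (E.2.b). E.2.d assumes a 20-point difference and makes no allowance for contamination.

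**The concern.** Finding a patient's barriers and referring the patient to someone who can remove them is what the enhanced arm is meant to add. If the same staff do this for usual-care patients because a questionnaire prompted it, part of the tested treatment reaches the comparator.

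The route to the outcome is direct. Referral to an insurance advisor or social worker acts on the barriers that keep people from appointments. The survey call asks how likely the patient is to attend a follow-up exam, and C.6.b presents the surveys as a way to strengthen engagement. In the sponsor's own randomized diabetes study (C.3.b), a package that included a navigator call raised attendance from 30% to 48%. That package was fuller than a survey call, but it is a reason not to treat such contact as inert.

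The expected bias is toward no effect. Table 7 counts NEI-VFQ referrals, and Table 8 counts low-vision, cataract and Medicare/Medicaid referrals, but neither asks for a split by arm. A null result could then not be told apart from a diluted one.

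**Working it through.** **1. Which contacts can matter**

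| Contact | Plan text | Could it affect Visit 4 and later? |
|---|---|---|
| Visit 2 NEI-VFQ | In person, by the research team, all patients; navigators act on results, no arm limit (C.6.a) | Yes, if results are acted on in Group 2 |
| Visit 5 NEI-VFQ | Phone, navigator or social worker, no arm limit (C.6.a) | Yes, mainly attendance after Visit 5 |
| Visit 5 satisfaction survey | Phone, same staff, both arms by name (C.6.b) | Yes, mainly attendance after Visit 5 |
| Visit 8 NEI-VFQ | Phone (C.6.a) or closeout visit (C.4.a) | No, follow-up is over |

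The Visit 5 contact with usual care is explicit. Referral in usual care follows only from the absence of an arm restriction.

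**2. Inputs**

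- Two-sided chi-square test (E.2.d). For the level, E.2.c says: "Each test will be performed with alpha=0.025".
- Analysed per arm: 150 × 0.9 = 135 (E.2.d). C.4.a instead randomizes 187 per arm; with the same 10% dropout, 187 × 0.9 = 168.3, about 168.
- Usual care 35% to 60%, intervention 20 points higher (Table 10).
- Assumed, not in the plan: usual care gains a share f of the 20 points, and the intervention rate is unchanged.

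**3. Formula**

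With p₁ = usual-care rate + 0.20f, p₂ = intervention rate and p̄ their mean:

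power = Φ{ [p₂ − p₁ − 2.2414·√(2p̄(1−p̄)/n)] / √([p₁(1−p₁) + p₂(1−p₂)]/n) }

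**4. The plan's own figure (f = 0, n = 135)**

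Row 40% v 60%: (0.20 − 2.2414 × 0.06086)/0.05963 = 1.067, and Φ = 85.7%. The six rows give 86.1, 85.7, 86.1, 87.2, 89.1 and 91.6%. Table 10 states 86, 86, 86, 87, 89 and 92%, so it reproduces in every row.

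**5. Dilution, row 40% v 60%, n = 135**

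- f = 0.10: p₁ = 0.42; (0.18 − 2.2414 × 0.06085)/0.05985 = 0.729; power 76.7%.
- f = 0.20: p₁ = 0.44; (0.16 − 2.2414 × 0.06081)/0.06002 = 0.395; power 65.4%. The relative risk falls from 0.60/0.40 = 1.50 to 0.60/0.44 = 1.36.

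**6. All six rows**

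| Assumed gain in usual care | 135 per arm | about 168 per arm |
|---|---|---|
| none | 86–92% | 93–96% |
| 2 points (f = 0.10) | 77–85% | 86–92% |
| 4 points (f = 0.20) | 65–76% | 76–85% |

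With 135 per arm, a 2-point gain puts four of the six rows below 80% and a 4-point gain puts all six below. With about 168, every row stays above 80% at 2 points, and four of the six fall below at 4 points.

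**The case against.** The strongest reply is that the plan never says usual-care patients are to be navigated. C.4.a, C.7 and C.8.a all attach these roles to the enhanced arm, so the referral sentence can fairly be read as covering only the patients whom the navigators serve. A questionnaire call is also not navigation: C.8 says that study staff generally have been trained as navigators, so the caller may simply be collecting data. The main active parts (reminder calls, scheduling, transport, interpreters, refill help) are nowhere extended to Group 2 by C.6.a or C.6.b. Timing narrows the exposure further, and referrals and fidelity are already tracked.

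Much of this stands. It rules out the stronger reading that a reader might infer, namely that the plan does deliver part of the intervention to controls and does dilute the result. The documents show a route, not an amount. They do not support any particular contaminated share, and Visit 8 is not a route at all.

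Two things remain. The Visit 5 call to both arms is stated outright, although C.6.b keeps usual care on mail at Visits 3, 4, 6 and 7. And C.6.a, which covers all patients, leaves staff free to act on usual-care results. The likely intent behind C.7 and C.8.a is a reason to reconcile the text; it does not override C.6.a.

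**Conclusion.** The point holds as a risk of unknown size. Followed as written, usual-care patients receive navigator or social-worker contact at Visit 5 and may receive barrier assessment and referral from Visit 2 onward. Any effect on attendance would bias the contrast toward no difference. Visit 2 results could touch both primary hypotheses; the Visit 5 calls mainly affect attendance after that visit.

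The power losses are illustrations. They assume that usual care gains 2 or 4 of the 20 points, that the enhanced arm is unchanged, and that the chi-square approximation of E.2.d stands in for the planned GEE model. The true gain could be close to nil, in which case Table 10 stands. The result also depends on which sample size applies, since C.4.a (187 per arm) and E.2.d (150 per arm) differ. Separately, C.4.a and C.6.a conflict on how the final NEI-VFQ is given.

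**What to change.** 1. Reconcile C.6.a and C.6.b with C.7, C.8.a and the closeout list in C.4.a. State which arm or arms receive action on NEI-VFQ results, and how the final NEI-VFQ is given. How needs found in Group 2 are handled is for the sponsor's clinicians to settle.
2. Have the Visit 5 questionnaires collected in both arms, with one neutral script, by existing study staff who are not acting as navigator or social worker for trial patients.
3. Report the navigator and social-worker contacts and the NEI-VFQ referrals in Tables 7 and 8 by arm, so that any contamination can be seen.

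The cost is protocol wording, an arm column in tracking that is largely planned already, and some reassignment of calls. The last is not free: C.8 says that many study staff are trained as navigators, so the sponsor must designate callers and keep the roles apart.
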